### 11. SUBJECT SELECTION

The study plans to enroll approximately 48 subjects with IgAN, LN, primary MN, or C3G (6-12 subjects per disease)

### 11.1. Inclusion Criteria

At specified screening and/or treatment visit(s) subjects must fulfill all of the following inclusion criteria to be eligible for participation in the study:

- 1. Patients of at least 18 years of age at screening (16 years of age for C3G), able to provide written informed consent, and able to understand and comply with all scheduled procedures and other requirements of the study by the opinion of PI
- 2. Patients must have a diagnosis of IgAN, LN, primary MN, or C3G confirmed by renal biopsy and required measurements performed prior to study participation
  - IgAN: Prior biopsy results for C3 and C4d staining should be made available
  - LN: Diagnostic biopsy showing proliferative focal, diffuse, or membranous lesions (Class III, IV, or V, respectively) by renal biopsy. Subject should have either a biopsy in the last 6 months, or evidence of disease activity (nephritic changes on urinalysis or nephrotic changes)
  - Primary MN: PLA2R positive titer plus nephrotic range proteinuria (defined as uPCR >2350 mg/g)
  - C3G plus one of the following: Low serum C3 level or historical renal biopsy within the last 3 years
- 3. Have proteinuria >750 mg/g uPCR (on 24-hour urine collection) collected during at the first screening visit (Visits 3a).
- 4. eGFR ≥30 mL/min/1.73 m² calculated by the Chronic Kidney Disease Epidemiology Collaboration (CKD-EPI) creatinine equation at Screening Visit 3a, currently not on dialysis.
- 5. Must have stable or worsening renal disease, on stable and optimized treatment, in the opinion of the PI, for at least 2 months prior to the first dose of pegcetacoplan (Visit 4); treatments may include, but are not limited to, immunosuppressive agents, antihypertensives and/or antiproteinurics.
- 6. Willing to receive vaccinations against *Neisseria meningitidis* at least 2 weeks prior to dosing on Day 1 with a booster on Day 56 (for both vaccinations) and pneumococcal and Hib vaccines at least 2 weeks prior to dosing on Day 1.
- 7. Women of childbearing potential (WOCBP) must have a negative blood pregnancy test at screening (and negative urine pregnancy at Visit 4) and must agree to use protocol defined methods of contraception from screening through 3 months after last dose of pegcetacoplan.

- 8. Males must agree to use protocol defined methods of contraception and agree to refrain from donating sperm from screening through 3 months after receiving last dose of pegcetacoplan.
- 9. Willing and able to give informed consent
- 10. Willing and able to self-administer pegcetacoplan (administration by caregiver will be allowed)

### 11.1.1. Approved Methods of Contraception

Approved methods of contraception include: oral contraceptives, intrauterine device, medically acceptable barrier methods (diaphragm or condom), implantable or injectable contraceptives (like Depo-Provera), or removable birth control device (like NuvaRing or Ortho Evra patches); and/or surgical sterilization (at least 6 months before dosing). Subjects practicing abstinence and coitus interruptus (pull out method) must agree to use an approved method of contraception during the study.

#### 11.2. Exclusion Criteria

Subjects will be excluded from the study if there is evidence of any of the following criteria at specified screening and/or treatment visits as appropriate.

- 1. Absolute neutrophil count <1000 cells/mm^3 at screening Visits 3a and 3b
- 2. Alanine aminotransferase (ALT) or aspartate aminotransferase (AST) >3.0× the upper limit of normal at screening Visits 3a and 3b
- 3. Previous treatment with pegcetacoplan
- 4. History of solid organ transplant
- 5. Diagnosis of human immunodeficiency virus (HIV), hepatitis B (HBV), or hepatitis C (HCV) infection, or positive serology at screening Visits 3a and 3b (previous HBV or HCV diagnosis cleared by treatment is allowed)
- 6. Malignancy except for cured basal or squamous cell skin cancer, curatively treated in situ disease, or have been disease-free for ≥5 years or more from cancer, and off ongoing treatment.
- 7. Renal disease secondary to another condition (eg, infection, malignancy, monoclonal gammopathy, or a medication)
- 8. Presence or suspicion of active bacterial or viral infection or severe recurrent bacterial infections
- 9. Participation in any other investigational drug trial or exposure to other investigational agent, device, or procedure within 30 days prior to screening period
- 10. Pregnant, breastfeeding, or intending to conceive during the course of the study
- 11. Inability to cooperate or any condition that, in the opinion of the investigator, could increase the patient's risk by participating in the study or confound the outcome of the study

- 12. Unwillingness to receive or intolerant of SC infusions of study medication or known allergy to ingredients in pegcetacoplan.
- 13. Positive results for drug abuse (upon urinary drug screen) or alcohol dependence at screening (Visit 3a). Documented evidence of prescribed marijuana use is not exclusionary.

### 12. STUDY TREATMENTS

### 12.1. Identity of Investigational Product

The test product is pegcetacoplan, which will be provided as a sterile solution of pegcetacoplan in acetate-buffered mannitol or sorbitol, supplied in stoppered glass vials. Additional information is provided in the pegcetacoplan IB. Investigational product will be administered as a 9-mL mannitol SC infusion (for 360-mg daily infusions) or as a 20-mL sorbitol SC infusion (for 1080-mg twice-weekly infusions).

### 12.2. Administration of Investigational Product

#### 12.2.1. Allocation to Treatment

All subjects who meet all the inclusion criteria and none of the exclusion criteria will receive open-label daily SC infusions of pegcetacoplan. Following completion of the 48-week treatment period, each subject will have the opportunity to enter Part B, the Long-Term Extension Phase (see Appendix 1 [Section A1.1]), at the discretion of the investigator. Any subject who does not enter Part B will enter the follow-up period, consisting of 6 clinic visits at Weeks 50, 52, 54, 60, 66, and 72 (Exit Visit).

### **12.2.2. Dosing**

Starting on Day 1 (Visit 4), subjects will receive self-administered daily SC doses of 360 mg of pegcetacoplan until at least Week 24 (Visit 11) and then as directed based on the timing of transition to twice-weekly dosing, and whether they are following Part A (Follow-up) or Part B (Long-Term Extension). Of important note, patients may be switched over to twice-weekly dosing with 1080 mg, as early as Week 24, but no later than the entrance into the extension phase of the study; timing of the switch is at the discretion of the sponsor. If dose transition occurs, the subject will need to follow the dose transition visits (T1, T2, and T3), as outlined in Section 10.1, Table 2 (Part A) or Appendix 1, Table A1 (Part B). The dose can be adjusted, as needed, to maintain clinical response, but no more than 1080 mg every third day.

### 12.2.3. Investigational Product Administration

Investigational product will be administered as an SC infusion. For more details on infusion duration, pump specifications, and utilization, please see the instructions for use and pharmacy manual.

The preferred site of injection will be the abdomen, however, if a subject does not tolerate administration into the abdomen, alternative appropriate sites may be considered. Research nurses or other appropriately qualified research personnel will administer the SC infusions at Visit 4 and will qualify and supervise the self-administration (or caregiver administration) for a minimum of 6 days until the subject has been qualified to conduct self-administration. During qualification the subject (or caregiver) must demonstrate to the research personnel their ability to safely and effectively administer study drug using the infusion pump. Following self-administration qualification, subjects may self-administer the SC infusions without supervision. Once qualified, the patient will continue to self-administer infusions at the clinic on those days when a clinic visit occurs and at an off-site location convenient to the subject on all other days.

Self-administration conducted at the clinic will be supervised to ensure that the subject continues to remain compliant with the administration guidelines.

Note: If the subject requires further training, the self-administration qualification period may be extended beyond 6 days. Self-administration may also be conducted by a member of the subject's household or family member, etc. who will undergo the same qualification criteria by the in-home medical professional (qualification is not intended to be restricted to the patient). Please refer to the Study Operations Manual for further details regarding the self-administration qualification.

### 12.3. Labeling, Packaging, Storage, and Handling

### 12.3.1. Labeling

Labels containing study information and pack identification are applied to the investigational product(s) container.

All investigational product is labeled with a minimum of the following: dosage form (including product name and quantity in pack), route of administration, directions for use, storage conditions, batch number and/or packaging reference, the statements "For clinical trial use only" and/or "CAUTION: New Drug – Limited by Federal (or US) Law to Investigational Use," and name and address of sponsor.

Space is allocated on the label so that the site representative can record a unique subject identifier and date dispensed by the site to the subject.

Additional labels may, on a case-by-case basis, be applied to the investigational product in order to satisfy national, local, or institutional requirements, but must not:

- Contradict the clinical study label.
- Obscure the clinical study label.
- Identify the study subject by name.

Additional labels may not be added without the sponsor's prior full agreement.

### 12.3.2. Packaging

Investigational product is packaged in the following labeled containers:

• 20-mL glass vials, 6 vials per carton.

Changes to sponsor-supplied packaging prior to dosing may not occur without full agreement in advance by the sponsor.

#### 12.3.3. Infusion Supplies

The sponsor will supply syringes, vial adapters, infusion sets, and ambulatory syringe infusion pumps as required. Refer to the Study Operations Manual for further details.

### 12.3.4. Storage and Handling

The investigational product should be stored refrigerated at 2-8 °C both at home and in the clinic.

The investigator has overall responsibility for ensuring that investigational product is stored in a secure, limited-access location at the site. Limited responsibility may be delegated to the pharmacy or member of the study team, but this delegation must be documented.

A pharmacist or appropriately qualified designated person will be responsible for storing the investigational product appropriately and dispensing the vials of investigational product to the subject. The pharmacist/nominated team member will enter the unique subject identifier on the investigational product bottle/carton labels as they are distributed.

Temperature monitoring is required at the investigator site (or documented storage location) to ensure that the investigational product is maintained within an established temperature range. The investigator is responsible for ensuring that the temperature in monitored throughout the duration of the study and that records are maintained.

The investigational product should be transported from the clinic to the subject's residence as described in the pharmacy manual, using the preconditioned phase change material plates and cooler bags. Temperature monitoring will not be required during transport or at the subject's residence, but a log will be kept for every infusion to ensure that all investigational product was kept refrigerated.

With sponsor prior approval, investigational product and/or ancillary supplies may be shipped from the study site to a subject's designated location. Such shipments will only be implemented at sites where this activity is approved by the IRB/EC and health authority (if required). Subject consent will be required prior to any subject information being provided to a courier. The responsibility to return both empty vials and any unused investigational product shall remain unchanged, as described in Section 12.5.

### 12.4. Investigational Product Accountability

Accountability for the study drug at the study center is the responsibility of the investigator, who must ensure that the study drug is used only in accordance with this protocol. Where allowed, the investigator may choose to delegate drug accountability responsibilities to a pharmacist or other appropriate individual.

Investigators will be provided with sufficient amounts of the investigational product to carry out this protocol for the agreed number of subjects. The investigator or designee will acknowledge receipt of the investigational product and document shipment content and condition. Accurate records of all investigational product dispensed, used, returned, and/or destroyed must be maintained. The investigator is responsible for ensuring the retrieval of all returnable study supplies from subjects. Study drug that has been dispensed to a subject and returned unused must not be re-dispensed to a different subject.

All unused and used study drug vials should be retained at the center until they are inventoried by the study monitor. At the conclusion of the study, any unused investigational product will either be destroyed at the investigator site or be returned to the sponsor or designee for destruction, and destruction will be documented appropriately. If no supplies remain, this fact will be documented appropriately.

### 12.5. Subject Compliance

Subjects must be instructed to bring their unused investigational product and empty/used investigational product packaging to every visit. The pharmacist/nominated person will record details on the drug accountability form.

### 12.6. Concomitant Medications

#### 12.6.1. Rescue Antibiotics

Body temperature, vital signs, and relevant blood parameters will be monitored regularly throughout the study to assess for signs of infection. The PI should be contacted immediately in the event of a suspected infection for guidance on appropriate action to be taken. Action to be taken may include administration of a broad-spectrum antibiotic to cover possible resistant organisms such as resistant pneumococcus (eg, levofloxacin).

### 13. STUDY PROCEDURES

Please see the Schedule of Events in Section 4 for Part A, the Core Study Phase, for a summary of the schedule of study participation and procedures. The schedule of visit dates should be established either prior to or at the time of screening, allowing subjects an opportunity to assess whether there are likely to be significant conflicts with other activities or planned absences. To the extent possible, subjects will be expected to adhere to the visit schedule and any re-scheduling of visits must be agreed, in advance, with the PI and sponsor.

A summary of the schedule of study participation and procedures for the Part B Long-Term Extension Phase is provided in Appendix 1, Table A1.

### 13.1. Screening (Week –4 to Week –2)

The subject will be screened to confirm that the subject selection criteria for the study has been met. Informed consent will be obtained at screening prior to any study-related procedures being conducted (see Section 17.3.3). Patients with sufficient previous medical history (see Section 10 for details) will begin the 4-week screening period.

A screen failure is a subject who has given informed consent and failed to meet at least one of the inclusion and/or met at least 1 of the exclusion criteria and has not been randomized or administered investigational product(s).

Screening procedures are listed in the Schedule of Events in Section 4.

The following assessments will be performed at each visit:

- Informed consent.
- Demographics
- Medical history (including current angiotensin-converting enzyme inhibitor/angiotensin-receptor blocker therapy) (Visit 3a only)
- Review of inclusion/exclusion criteria
- Physical examination
- Begin 24-hour urine collection during scheduled clinic visit (Visit 3a only)
- Triplicate 12-lead ECG
- Prior and concomitant medications
- Vital sign measurements
- Urinalysis assessment (see schedule of events for details)
- Blood tests (see schedule of events for details)
- β-HCG pregnancy test, if applicable
- Follicle-stimulating hormone, HIV, HCV, HBsAg (see schedule of events for details)
- AE collection
- Vaccination Titer Serum Sample (Visit 3b only)

- Vaccination (see schedule of events for details)
- Dispense 3 uPCR containers for consecutive collection (Visit 3b only)

#### 13.1.1. Vaccinations

Subjects will be required to be vaccinated as follows, according to Advisory Committee on Immunization Practices (ACIP) recommendations for vaccination in patients with immunocompromising conditions (available at

https://www.cdc.gov/vaccines/schedules/hcp/imz/adult-conditions.html).

- Neisseria meningitidis types A, C, W, Y: Menactra®. First dose at least 2 weeks prior to dosing (Day –14) with a booster after 2 months (Day 56).
- *Neisseria meningitidis* type B: Bexsero®. First dose at least 2 weeks prior to dosing (Day -14) with a booster after 2 months (Day 56).
- Streptococcus pneumoniae: Prevnar 13®(PCV13) at least 2 weeks prior to dosing (Day -14) and Pneumovax® (PPSV23) after 2 months (Day 56).
- Haemophilus influenzae type B: ActHIB® at least 2 weeks prior to dosing (Day -14).

Vaccination is mandatory, unless documented evidence exists that subjects have received all recommended vaccines or are nonresponders to vaccination. All required vaccination(s) for which evidence is not available will be administered as needed to bring subjects up to date. The investigator should discuss with the medical monitor any individual patient circumstances that are relevant to the vaccination requirements or that would make the above schedule not possible or reasonable. On an ongoing basis, including upon entry into the long-term extension phase, subjects should be reevaluated for the need for any vaccinations based on ACIP recommendations. Subjects who withdraw from the study prior to any vaccine booster will be offered the opportunity to return to the site as recommended by current ACIP Adult Immunization schedule to receive the booster shot.

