## 4. SCHEDULE OF EVENTS

Table 1, below, represents the Schedule of Events for Part A, the Core Study Phase. The Study Flow Chart for Part B (Long-Term Extension Phase) is provided in Appendix 1 (Section A1.1).

Table 1: Schedule of Events, Part A, Core Study Phase

Study Period	Per	ening iod: eeks a		Treatment Period: 48 Weeks								Follow-up & Exit: 24 Weeks								
Study Week	-4	-2	1	2	4	8	12	16	20	24	30	36	42	48	50	52	54	60	66	72 (Exit)
Study Day	-28	-14	1	14	28	56	84	112	140	168	210	252	294	336	350	364	378	420	462	504
Study Visit	3a	3b	4	5	6	7	8	9	10	11	12	13	14	15	16	17	18	19	20	21
Visit Window (±Days)	0	3	0	2	2	2	2	2	2	2	2	2	2	2	2	2	2	7	7	7
Informed Consent	X																			
Demographics	X																			
Medical History	X																			
Inclusion/Exclusion b	X	Х	X																	
Vaccination c		Х				X														
Concomitant Medications	X		X	X	X	X	X	X	X	X	X	Х	X	X	X	X				
Physical Examination d	X		X	X	X	X	X	X	X	X	X	X	X	X	X	X				
12-Lead Electrocardiogram e	X		X	X	X	X	X	X	X	X	X	X	X	X	X	X	X	X	X	Х

Table 1: Schedule of Events, Part A, Core Study Phase

Study Period	Scree Per 4 We			Treatment Period: 48 Weeks									Follow-up & Exit: 24 Weeks							
Study Week	-4	-2	1	2	4	8	12	16	20	24	30	36	42	48	50	52	54	60	66	72 (Exit)
Study Day	-28	-14	1	14	28	56	84	112	140	168	210	252	294	336	350	364	378	420	462	504
Study Visit	3a	3b	4	5	6	7	8	9	10	11	12	13	14	15	16	17	18	19	20	21
Visit Window (±Days)	0	3	0	2	2	2	2	2	2	2	2	2	2	2	2	2	2	7	7	7
Investigational Drug Product Administration (Daily) f				Daily Administration>																
Injection Site/Infusion Pump Safety Assessment g			X	х	Х	Х	Х	Х	х	Х	х	х	х	Х	Х					
Vital Sign Measurements h	Х	Х	Х	Х	X	X	Х	Х	X	X	Х	Х	Х	X	X	Х	Х	X	Х	х
Urine																				
24-Hour Urine Collection i	Х													X						х
Dispense uPCR containers		Х	X	Х	Х	X	Х	Х	Х	Х	Х	Х	Х	Х	Х	Х	Х	Х	Х	
Return uPCR samples j			Х	Х	х	Х	Х	Х	Х	Х	Х	Х	Х		Х	Х	Х	Х	Х	
Arrange home uPCR Courier pickup k					X	X	X	X	X	X	Х	Х	X				Х	X	X	
Urinalysis– microscopic & Dipstick i	Х	Х	Х	Х	Х	Х	Х	Х	Х	Х	Х	Х	Х	Х	Х	Х	х	Х	Х	х

Table 1: Schedule of Events, Part A, Core Study Phase

Study Period	Per	ening iod: eeks a	Treatment Period: 48 Weeks												Follow-up & Exit: 24 Weeks						
Study Week	-4	-2	1	2	4	8	12	16	20	24	30	36	42	48	50	52	54	60	66	72 (Exit)	

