- b Specific inclusion/exclusion criteria will be measured during screening, and some of them require confirmation on Visit 4 (Day 1) prior to performing any activities of Day 1 procedures. See the inclusion/exclusion criteria in Section 11 for further detail.
- c Neisseria meningitidis vaccine(s) will be administered during screening (Day –14); a booster for Neisseria vaccination(s) should be administered at Visit 7. Additionally, pneumococcal vaccine PCV13 will be administered at least 2 weeks prior to Day 1, and a dose of PPSV23 will be administered at least 8 weeks later unless documented evidence exists that patients are nonresponders to vaccination as evidenced by titers or display titer levels within acceptable local limits. Haemophilus influenzae Type B (Hib) vaccinations will be administered at Day –14. Subjects who withdraw from the study prior to any vaccine booster will be offered the opportunity to return to the site as recommended by current CDC Adult Immunization schedule to receive the booster shot. Subjects who are being rescreened for the trial will not require repeat vaccination for those vaccines documented as given during a previous screening visit.
- d Full physical examination will be performed at Visits 4 and 15. Brief physical examinations will be conducted at all other clinic visits as noted above in the schedule of events. A symptom-driven physical examination may be performed at other times, at the PI's discretion. (Body height [cm] and weight [kg] will be measured at Visit 3a, and body weight will be measured throughout study, during brief and full physical examinations.)
- e Triplicate 12-lead ECGs (which have a ±5-minute start window) are to be performed: D1 (V4) and Week 48 (V15): -45, -30, -15 minutes predose and before dosing at all other treatment visits. Once each triplicate ECG begins, subsequent ECGs should be at least one minute and no more than 2 minutes apart. During screening and follow-up periods, triplicate ECGs will be collected immediately after vital measurements.
- f Patients will self-administer SC pegcetacoplan after receiving appropriate training and sign-off by a research nurse or other personnel in their first treatment week. During site visits patients will self-administer pegcetacoplan at the site, with the exception of the very first dose.

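### The ±3-day window on Visit 3b admits vaccination days that fall short of the protocol's written two-week minimum before first dose

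*Protocol*

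**What the plan says.** Four places in the protocol bear on the interval.

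- **Section 13.1.1** applies the two-week minimum to each vaccine due before treatment: both meningococcal vaccines, PCV13 and Hib. The wording for the meningococcal vaccines is "First dose at least 2 weeks prior to dosing". Day -14 is given in brackets as the nominal day.
- **Table 1 (Section 4)** marks vaccination at Visit 3b. For Visits 3a, 3b, 4 and 5 its rows read "Study Day -28 -14 1 14" and "Visit Window (±Days) 0 3 0 2". Visit 3b is therefore Day -14 ±3, and Visits 3a and 4 have no window.
- **Footnote c to Table 1** states a minimum for one vaccine only: "pneumococcal vaccine PCV13 will be administered at least 2 weeks prior to Day 1". For the meningococcal vaccines it says "vaccine(s) will be administered during screening (Day –14" and gives no minimum. It handles Hib in the same way, by day alone.
- **Inclusion criterion 6 (Section 11.1 and synopsis)** repeats the interval, ending "vaccines at least 2 weeks prior to dosing on Day 1". What it tests is the subject's willingness to be vaccinated on that timing.

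Section 14.1.9.6 also ties vaccination to Visit 3b, because the titer sample taken there comes before vaccination. Section 12.2.2 starts dosing on Day 1 at Visit 4.

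**The concern.** The nominal day equals the minimum, and the window is symmetric around it. The late half of the window therefore lies below the minimum, and neither the window row nor footnote c restricts the late side.

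Two things are at stake. The first is safety: Section 8.3 names vaccination as a measure against infection with encapsulated organisms under complement inhibition, so this interval has a protective purpose. The second is deviation handling: a Visit 3b on Day -11 is in window by Table 1 but breaches Section 13.1.1. SAP Section 5.7 allows deviations to be found by programmed checks and tabulates them for Part A + B. A check built on the visit window would pass this visit, while one built on Section 13.1.1 would flag it. The vaccination summary in SAP Section 5.2.4 counts vaccines received and does not examine the interval to first dose, so it would not show the shortfall either.

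**Working it through.** **Inputs.** Visit 3b nominal day -14 and window ±3; Visit 4 on Day 1 with window 0 (Table 1). Minimum interval 2 weeks = 14 days (Section 13.1.1).

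**Study-day convention.** For days before the first dose, SAP Section 13.2 sets study day = visit date − date of first dose. There is no Day 0, so Day -k is k days before the first dose. The protocol states no convention, and the window tables in SAP Sections 13.4.2 and 13.4.3 run to 0, so the variant with a Day 0 is shown as well.

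- No Day 0: days before first dose = −(study day)
- With Day 0: days before first dose = 1 − (study day)

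**Plan's own figure.** Day -14 gives −(−14) = 14 days, which reproduces the equation of Day -14 with two weeks. The slack is 14 − 14 = 0 days.

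**Every day in the window**, from −14 − 3 = −17 to −14 + 3 = −11:

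| Visit 3b on | Days before dose, no Day 0 | Days before dose, with Day 0 |
|---|---|---|
| Day -17 | 17 | 18 |
| Day -16 | 16 | 17 |
| Day -15 | 15 | 16 |
| Day -14 | 14 | 15 |
| Day -13 | 13 (short) | 14 |
| Day -12 | 12 (short) | 13 (short) |
| Day -11 | 11 (short) | 12 (short) |

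**Result.** Under the SAP convention, 3 of 7 permitted days fall short, the worst by 14 − 11 = 3 days. With a Day 0, 2 of 7 fall short, the worst by 14 − 12 = 2 days. The conflict exists either way.

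The 3 of 7 counts permitted days. It does not estimate the share of subjects vaccinated late, about which the documents say nothing.

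**The case against.** The strongest reply is that a visit window says when a visit may take place and does not waive a separate written minimum. Section 13.1.1 states that minimum for every vaccine due before treatment. A site that doses 11 days after vaccination has breached the protocol, whatever the window row says. This stands. A reader might infer that the protocol permits dosing before two weeks, or that a site following all of it correctly could do so. The documents do not support that.

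A reader might also infer that Section 13.1.1, footnote c and inclusion criterion 6 all impose the minimum on every vaccine. They do not: footnote c states it only for PCV13, and criterion 6 concerns willingness.

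A second reply is that Day 1 is by definition the day of first dose, that screening lasts only approximately 4 weeks, and that Section 13 allows visits to be rescheduled by agreement. A late Visit 3b could then be met by a later first dose. This is a workable route in an individual case, but it does not cure the table. Postponing the dose by 3 days moves a Day -11 visit back to Day -14, and it also moves Visit 3a from Day -28 to Day -31, where its window is 0. A visit that is still labelled Day -11 remains 11 days before dosing.

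Other provisions narrow the reach. Section 13.1.1 exempts subjects with documented vaccination and nonresponders, and footnote c spares rescreened subjects a repeat. Individual difficulties go to the medical monitor. Eligibility is confirmed again at Visit 4, although the Section 13.2.1 list does not mention checking the actual interval. Vaccination is also not the only safeguard: Sections 8.3 and 12.6.1 add infection monitoring, contact with the investigator and possible antibiotics. None of this aligns the routine window with the minimum.

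Finally, the mismatch concerns Part A screening. The Amendment 7 summary reports that C3NeF testing in Part A is complete, and SAP Section 1 says that SAP version 1.0 was used for the Part A analysis. This limits what an edit can still protect.

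**Conclusion.** The internal inconsistency is real and should be corrected. Its practical weight is modest. Table 1 admits three vaccination days (Days -13 to -11) that give 13 to 11 days against a written minimum of 14. With a Day 0 counted, two days fall short. The result rests on reading two weeks as 14 days and on taking the windows of 0 at Visits 3a and 4 as printed.

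The risk is that a site scheduling from the window alone breaches Section 13.1.1 without noticing, and that the documents leave the deviation status of that visit open. It is confined to subjects who need vaccination during screening. The documents do not show that any subject was dosed early, and none should be assumed. With Part A apparently complete, the live question is mainly how such visits are classified in the Part A + B deviation table, which covers the subjects who rolled over.

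**What to change.** Reconcile the Visit 3b window in Table 1, and footnote c, with Section 13.1.1 and inclusion criterion 6 in Section 11.1 and the synopsis, so that no visit within window can breach the stated minimum. Footnote c should treat all the vaccines due before dosing consistently with Section 13.1.1. Which passage changes, and how, is the sponsor's choice.

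State also, in the protocol or the deviation management plan cited in SAP Section 5.7, which passage governs the classification of a Visit 3b that is in window but less than two weeks before first dose. Apply that rule to subjects already enrolled.

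The cost is an edit to one table and its footnote, plus one sentence on deviations. The downside is a small loss of scheduling flexibility in screening.
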